## **INITIAL PATIENT EVALUATION**

The following medical evaluations and laboratory samplings will be performed for patients of both study groups at the investigational centre, and while the patient is in stable state (*defined by a period of at least 3 weeks without exacerbation*):

- Medical evaluations (*as detailed in sections 6.A.2.5 and 6.B.1*)
  - ✓ Post-bronchodilator pulmonary function tests (*spirometry*),
  - ✓ Six-minute walk test on room air or on oxygen for patients on oxygen therapy,
  - ✓ Transthoracic Doppler echocardiography,
  - ✓ 12-lead supine resting electrocardiogram.

- Laboratory samplings (*as detailed in section 6.B.2*)
  - ✓ Resting arterial or capillary blood gases on room air,
  - ✓ Venous blood sampling for measurements of haemoglobin, haematocrit and C-Reactive Protein (CRP).

Medical tests and laboratory samplings that were routinely performed before Selection and signature of the Informed Consent can be used for initial patient evaluation: they will not have to be repeated if performed within 3 months before randomisation, in stable clinical conditions, and if all parameters to be reported in the eCRF had been collected.

Initial patient evaluation should be completed before Visit 1 and all results will be recorded by the investigator in the e-CRF at Visit 1.

## COPD EDUCATION

**Patients randomised in the Control group** will receive the usual COPD education as per investigational centre routine practice. The content and modalities of each centre will be collected before study initiation, as well as any modifications throughout the study period, if applicable.

**Patients randomised in the Intervention group** will undergo four (4) individual home education sessions, performed on a weekly basis by a community-based health professional (*called for the study 'health counsellor' and detailed in section 5.A.1*):

- The four sessions will be performed before Visit 1, in a minimum of 3 weeks and a maximum of 5 weeks after randomisation.
- Each individual session is planned to last 60 to 90 minutes during which the health counsellor will use specific teaching material in local study language and will give the patient the printed education documents (*handbooks and brochure, as detailed in section 5.A.1.1*) and the study medical devices (*portable pulse oximeter, spirometer and thermometer, as detailed in section 5.A.4*). The patient will also be trained to perform phone calls to the study dedicated vocal server. After each education session, the understanding and skills of the patient will be assessed and a report will be sent by the health counsellor to the investigator concerned.

## VISIT AT THE INVESTIGATIONAL CENTRE (*VISIT 1*)

Before seeing the investigator, patients will complete on their own **the three (3) following questionnaires** (*as detailed in section 6.A.2.4 and 6.A.2.7 and provided in Appendix 3*):

- The COPD-specific version of the St George's Respiratory Questionnaire (*SGRQ-C*),
- The 15D health-related quality of life instrument (*available from: <http://www.15d-instrument.net>*),
- The Hospital Anxiety and Depression Scale (HADS).

Validated versions of these three (3) questionnaires in the four (4) study languages (*German, French, Italian and Spanish*) will be used.

**During Visit 1**, the investigator will record the following data in the e-CRF:

- Date of Visit 1,

- Results of the physical examination including vital signs (*i.e.*, *systolic and diastolic blood pressures*), weight and pulse oximetry (*pulse rate and SpO2*) on room air and also on oxygen for patients on oxygen therapy,
- Changes in social conditions, if applicable,
- Changes in smoking status, if applicable,
- Recovery from concomitant diseases since Visit 0, if applicable,
- Assessment of the severity of dyspnoea using the modified Medical Research Council Dyspnoea Scale ,
- Comorbidities to allow the calculation of the Charlson Comorbidity Index ,
- Changes in COPD and non-COPD medication, including oxygen therapy, CPAP, Non-Invasive Ventilation and vaccines (*as detailed in section 5.D*), since Visit 0, if applicable,
- Occurrence of COPD exacerbations (*as defined in section 6.A.2.2*) since Visit 0,
- Occurrence of other Adverse Events (*see section 6.B*) since Visit 0,
- Results and dates of the medical evaluations and laboratory samplings performed during the *Run-In Period*,
- Serial number of the *NOWOX* device assigned to the patient, if applicable.

**At the end of the visit**, if the patient is on oxygen therapy, the investigator will give to the patient the *NOWOX* medical device, after having initialised it and having explained to the patient its correct use (*see section 5.A.4.1*). All patients on oxygen therapy will receive the *NOWOX* user manual and simplified user sheet in their native language and they will be instructed to wear the *NOWOX* each time they use oxygen therapy and to bring it at each of their study visits at the investigational centre.

#### 4.B.3.2. Follow-Up Period

The *Follow-Up Period* starts at the end of Visit 1 and will last 12 months for each patient.

Patients will undergo during this period:

- **Visits** at the investigational centre every 3 months (*Visits 2 to 5*),
- **Standardised phone interviews** performed by an investigational centre staff member every 3 months between the patient visits at the investigational centre (*Centre phone contacts 1 to 4*),
- And, **for patients randomised in the Intervention group**, education sessions given by a health counsellor every month (*alternatively group and phone sessions*), and an at least weekly prospective telephone follow-up while **for patients randomised in the Control group**, the usual COPD education and follow-up as per investigational centre routine practice.

## **VISITS AT THE INVESTIGATIONAL CENTRE (*VISITS 2 TO 5*)**

**Visits 2 to 5** are scheduled at Month 3, Month 6, Month 9 and Month 12 from Visit 1, respectively. These visits may vary from their planned timelines starting at Visit 1 by  $\pm 30$  days, without modifying the initially planned timelines of the following visits if a given visit needs to be advanced or postponed.

**During Visits 2 to 5**, the investigator will record the following data in the e-CRF:

- Date of Visit,
- Results of the physical examination including vital signs (*i.e.*, *systolic and diastolic blood pressures*), weight and pulse oximetry (*pulse rate and SpO2*) on room air and also on oxygen for patients on oxygen therapy,
- Changes in social conditions, if applicable,
- Changes in smoking status, if applicable,
- Recovery from concomitant diseases since the last visit, if applicable,
- Changes in COPD and non-COPD medication, including oxygen therapy, CPAP, Non-Invasive Ventilation and vaccines (*as detailed in section 5.D*), since the last visit, if applicable,
- Occurrence of COPD exacerbations (*as defined in section 6.A.2.2*) since the last visit,
- Occurrence of other Adverse Events (*see section 6.B*) since the last visit,
- For patients on oxygen therapy, checking of the *NOWOX* device (*to detect the need for an exchange or return of the device at study end*), and, if applicable, the reason for exchanging or returning the *NOWOX* device and the serial number of the new *NOWOX* device assigned, whenever necessary; of note, patients starting oxygen therapy during their study participation will be given a *NOWOX* following the procedure described in section 4.B.3.1 and their start date and criteria for oxygen prescription will be collected, as described in section 4.B.1.2.
- Use of health care services (*see section 6.A.2.3*) since the last visit.

**At Visit 3 (Month 6) and Visit 5 (Month 12 or study end in case of premature withdrawal)**, additional questionnaires and examinations will be performed as follows:

- The SGRQ-C, 15D and HADS questionnaires (*as detailed in sections 6.A.2.4 and 6.A.2.7 and provided in Appendix 3*), self-administered before the consultation with the investigator at **Visit 3 (M6)** and **Visit 5 (M12)**,
- Assessment of the severity of dyspnoea using the modified Medical Research Council Dyspnoea Scale at **Visit 5 (M12)**,
- Comorbidities to allow the calculation of the Charlson Comorbidity Index at **Visit 5 (M12)**,

Medical evaluations (pulmonary function tests, six-minute walk test on room air or on oxygen if the patient is on oxygen therapy, transthoracic Doppler echocardiography and ECG, as detailed in sections 6.A.2.5 and 6.B.1) performed while the patient is in stable state (defined by a period of at least 3 weeks without exacerbation) performed between **Visit 4** (M9) and **Visit 5** (M12), and recorded by the investigator in the e-CRF at **Visit 5**,

- Laboratory samplings (*as detailed in section 6.B.2*): resting arterial or capillary blood gases on room air and venous blood sampling (*for measurements of haemoglobin, haematocrit and CRP*) performed between **Visit 4** (M9) and **Visit 5** (M12), and recorded by the investigator in the e-CRF at **Visit 5**,
- Collection at **Visit 5** (M12) by the investigator of the *NOWOX* device, if applicable, and all other study medical devices provided to the patient of the Intervention group (*i.e, the portable pulse oximeter, spirometer and thermometer*).

## **STANDARDISED PHONE INTERVIEWS BY AN INVESTIGATIONAL CENTRE STAFF MEMBER**

Standardised phone contacts will be scheduled every 3 months between the patient and a staff member of the investigational centre to collect information regarding the patient use of health care services (*medical and paramedical consultations, attendances at emergency departments, hospitalisations, ...*). Four (4) phone interviews (*Centre phone contacts 1 to 4*) will be scheduled respectively at Month 1.5, Month 4.5, Month 7.5 and Month 10.5 from Visit 1 (*each phone contact may vary from its planned timeline by  $\pm 15$  days, without modifying the initially planned timelines of the following phone contacts, nor the planned schedule of the patient visits at the investigational centre*).

During the standardised phone interviews, the patient will be asked to read his/her notes in the "Patient's Study Diary" (*see section 4.B.1.2*) since the last visit at the investigational centre. The information collected through a standardised questionnaire in local language will be recorded in the e-CRF by the investigational centre staff member in charge of the interview and validated by the investigator. At the end of each phone interview, the patient will be reminded of the date and time of his/her next visit at the investigational centre and, if applicable, to bring back the *NOWOX* device.

## **EDUCATION AND FOLLOW-UP**

**Patients randomised in the Control group** will receive the usual COPD education and follow-up as per investigational centre routine practice.

**Patients randomised in the Intervention group** will attend education sessions (*alternatively group and phone sessions*) dispensed by the health counsellor and will undergo a prospective telephone follow-up:

- Group education sessions

The first group education session will be scheduled 2 months after Visit 1, and thereafter every 4 months until Month 12. Each group education session will last about two hours and will be animated by two (2) health counsellors who will use specific teaching material in local language (*described in section 5.A.1.1*). The main aim of these group education sessions is to reinforce the patients' knowledge and skills regarding their action plan.

- Phone education sessions

The first phone education session will be scheduled 1 month after Visit 1 and thereafter every month (*except months when a group session is performed*) until Month 12. Supplemental phone education sessions will be scheduled if a COPD exacerbation occurs or on patient's request. Each phone education session will last about half an hour and aims to assess/reinforce the specific skills and behaviours that the patient needs to acquire and to maintain over time, *i.e.*, in particular the importance of self-evaluation and regular symptoms reporting, and the procedures that will be implemented in case of a clinical deterioration.

- Prospective telephone follow-up

Patients will be instructed to phone to the study dedicated vocal server to report their clinical status (*as detailed in section 5.A.1.2 and Appendix 2*) at least once a week (*and at most once a day*), and each day their clinical status is worse than usual.

In case they report a deterioration of their overall clinical status, patients will be asked to perform a home respiratory self-assessment (*pulse oximetry, spirometry, and temperature*) and to report the results of their measurements in their study diary. They will be called back by a health counsellor within 2 hours following their telephone report (*or on the first following working day if the report occurs during week-end or public holiday*). The health counsellor will review the questionnaire with the patient, validate it, collect additional parameters via a second questionnaire including the results of the patient's respiratory self-assessment and provide the patient with adequate reinforcement and counselling. If a significant deterioration of the patient's clinical status is confirmed (*scoring methodology is provided in Appendix 2*), the investigator in charge of the patient follow-up will be informed, so as to take the appropriate medical decision and communicate it to the patient on the same day.

#### **4.B.4 Evaluation of protocol compliance**

Any deviations of protocol procedures described in section 4.B.3 will be reported in the e-CRF of the patients concerned, together with any other abnormalities or incidents occurring during the study.

Protocol deviations correspond to non-compliance with the protocol (*e.g., non-compliance with the study procedures, the follow-up duration, the attendance to the education sessions or the prospective telephone follow-up, etc...*). Such deviations do not require the patients concerned to be withdrawn from the study but the corresponding data must be recorded in the e-CRF. The impact of all encountered deviations on the evaluation criteria will be assessed by the sponsor study personnel, prior to the database lock. The sponsor study personnel will also decide whether a Per Protocol data set needs to be defined prior to the start of the statistical analysis (*see section 7.B.3.1*).

#### **4.B.5 Study premature withdrawals**

If at any time the study procedures are considered compromised, the concerned patient may be withdrawn from the study at the investigator's discretion. Moreover, patients are free to discontinue their participation in the study at any time as described in their Informed Consent.

The reason and date of study premature withdrawal will be recorded in the e-CRF of the patients concerned (*e.g., consent withdrawn, death, etc...*) by the investigator. As mentioned in section 3.D, patients who are prematurely withdrawn from the study during the *Follow-Up Period* will not be replaced.

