### 3.D WITHDRAWAL CRITERIA

Reasons for **premature discontinuation of the allocated management strategy** include:

- Patient moving for long term stay in a medicalised nursing home,
- Any lack of compliance to the study procedures which can compromise the study progress, and, in particular, for the Intervention group only:
  - a) Absence of phone call to the study vocal server to report clinical status for more than 1 month for another reason than being away from home,
  - b) Refusal or inability to follow the four individual home education sessions before Visit 1 as detailed in section 4.B.3.1.

Whenever possible, in case of premature discontinuation of the allocated management strategy, patients will be followed up until Month 12 as initially planned (*by regular visits at the investigational centre and standardised phone interviews, as detailed in section 4.B.3.2*).

Reasons for **study premature withdrawal** include:

- Patient moving away from the geographic area of the investigational centre resulting in the patient's inability to attend study visits,
- Withdrawn consent as described in the Patient Informed Consent,

- Death.

The reason, date and time for premature discontinuation of the allocated management strategy and/or study premature withdrawal will be recorded in the electronic Case Report Forms (e-CRF) of the patients concerned by their investigator. Survival data until Month 12 will be collected unless the patient disagrees.

**The patient will be replaced** only if premature discontinuation of the allocated management strategy or study premature withdrawal occurs before the end of Visit 1 (*see section 4.B.3.1*).

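### Section 4.B.5 lets an unblinded investigator end study participation where section 3.D stops only the allocated strategy, and no collection of hospital days is stated after such an exit

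*Protocol*

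**What the plan says.** - **Protocol 4.B.5** gives the investigator an exit from the study: "If at any time the study procedures are considered compromised, the concerned patient may be withdrawn from the study at the" investigator's discretion. It adds no criterion and no duty to continue follow-up. It requires the reason and date to be recorded.
- **Protocol 3.D** lists, among the reasons for stopping the allocated strategy, "Any lack of compliance to the study procedures which can compromise the study progress, and, in particular, for the Intervention group only", followed by two named triggers: no call to the vocal server for more than a month (unless away from home), and refusal of or inability to follow the home sessions before Visit 1. For patients who stop the strategy it says that, whenever possible, "patients will be followed up until Month 12 as initially planned".
- **Protocol 3.D** gives separate reasons for leaving the study: moving away, consent withdrawn ("Withdrawn consent as described in the Patient Informed Consent") and death. Investigator discretion is not among them. For the time after either kind of exit it states: "Survival data until Month 12 will be collected unless the patient disagrees". It does not mention hospital days.
- **Protocol 4.B.4**, on deviations: "Such deviations do not require the patients concerned to be withdrawn from the study".
- **Protocol 4.B.2** states that neither patients nor centre staff are blinded after randomisation.
- **Protocol 7.B.3.5** multiplies recorded unscheduled hospital days by 365 over the patient's days in the Follow-Up Period, and compares the groups with the Wilcoxon rank-sum test on the ITT set. Under 7.B.3.1 that set is every randomised patient who entered the Follow-Up Period.

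**The concern.** Two sections attach different consequences to closely similar situations, and nothing gives one precedence. Two centres could treat identical patients differently, one keeping the patient in follow-up and the other ending participation, and both would comply.

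The difference reaches the primary endpoint. A patient who only stops the strategy goes on contributing hospital days. A patient withdrawn from the study does not, and the analysis uses the earlier rate in place of the unobserved remainder of the year. The decision is taken by someone who knows the allocation and probably also how the patient is doing. If such exits are more frequent in one arm, or fall on patients whose later course is worse than their earlier one, the comparison is biased. A statistical analysis plan can choose how to handle the missing days but cannot recover days that were never collected.

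**Working it through.** **1. The passages side by side**
- Trigger. 3.D: non-compliance that can compromise the progress of the study. 4.B.5: procedures considered compromised.
- Consequence. 3.D: the strategy stops. 4.B.5: the patient may leave the study.
- Later hospital days. 3.D: collected to Month 12 whenever possible. 4.B.5: no collection stated.
- Who decides in 4.B.5: the investigator, unblinded, without further criteria.

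**2. What annualising does to an early exit**

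Formula (7.B.3.5): analysed value = D × 365 / F, rounded, where D is recorded unscheduled hospital days and F is days of follow-up. The protocol's own example reproduces: 18 × 365 / 182 = 36.1, taken as 36.

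Suppose this patient would have had x further hospital days in the remaining 365 − 182 = 183 days. The full-year total is 18 + x, and the error of the analysed value is 36 − (18 + x) = 18 − x. The value is right only if the second half resembles the first. It understates if the patient gets worse (x > 18) and overstates if the patient improves (x < 18). The direction is not fixed by the documents.

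**3. Lost numbers are not the main issue**

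Inputs (7.B.2): difference 10 days, SD 25, two-sided α 0.05, power 0.90.
- p = Φ(10 / (25√2)) = 0.6114.
- Noether formula: n per group = (1.960 + 1.282)² / [6 × (0.6114 − 0.5)²] = 141.2, so 142. The stated figure is 143.
- 143 / (1 − 0.0625) = 152.5, so 153 per group and 306 in total, as stated.
- Power from 153 randomised per group, by a rank-sum formula using the variance under the alternative: 0.91 with 6.25% lost, 0.90 with 10%, 0.88 with 15%, 0.84 with 25%.

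The sample size stands. What matters is who is lost.

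**4. How far selectivity could matter (illustration only)**

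None of these assumptions is in the protocol: no true effect; 1.3 stays per patient-year with gamma frailty of shape 0.6; mean stay 10 days; 153 per arm; exits in the Intervention arm only; 2,000 simulated trials per setting. With no exits the rejection rate was 4.75% and 4.85% in the two settings.

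| Intervention arm withdrawn | Exits favour high-risk patients, no endpoint data left: rejection rate; spurious difference in means | Exits unrelated to risk, days annualised: rejection rate; difference in means |
|---|---|---|
| 6.25% | 9.0%; 1.3 days | 5.6%; 0.1 days |
| 10% | 11.8%; 2.0 days | 6.3%; 0.0 days |
| 15% | 20.5%; 3.0 days | 6.3%; 0.1 days |

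The simulation standard error at a 5% rate is √(0.05 × 0.95 / 2000) = 0.5 percentage points. The middle column is deliberately adverse. It needs one-arm, risk-related exits that leave no usable endpoint data, which 7.B.2 assumes only for dropouts before Visit 2.

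**The case against.** The strongest reply is that the sections can be read together: non-compliance ends the strategy under 3.D, and 4.B.5 is a residual discretion for other cases. Its verb is permissive, it claims no precedence, and the list of study-withdrawal reasons in 3.D is introduced as inclusive, so it is not closed. The supportive three-group analysis in 7.B.3.1 also expects patients who stop the strategy yet complete the study. Dropouts are to be described by group, time and reason, with a log-rank comparison (7.B.3.3), so lopsided exits would be seen.

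Much of this stands, and it limits the point:
- A reader might infer that 4.B.5 overrides 3.D. Nothing says so. The text is silent on precedence, and that silence is the defect.
- A reader might infer that 4.B.4 contradicts 4.B.5. It does not. Saying that withdrawal is not required is compatible with allowing it, and 4.B.4 does not itself order follow-up. The two are in tension only.
- A reader might count both Intervention-only triggers in 3.D as routes to annualised partial data. The home-session trigger arises before Visit 1, when there are no Follow-Up days to annualise, and 3.D provides for replacement of that patient. Only the missed-call trigger fits the mechanism.
- A reader might infer that exits will fall mainly on the Intervention group. 4.B.5 is not arm-specific, and the general non-compliance clause of 3.D covers both arms. Imbalance is possible but not established.

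What the reply does not answer: 4.B.5 gives no wording that confines it to cases outside 3.D, and a description of dropouts shows an imbalance without restoring the missing days. The Endpoint Validation Committee (6.D) reviews reported hospitalisations, so it cannot recover them either.

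**Conclusion.** The conflict between 3.D and 4.B.5 is real, and it concerns data collection for the primary endpoint in an open-label trial. It is worth correcting as a cheap improvement. It does not show that the trial is biased.

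The loss is partial. A reader might infer that a withdrawn patient drops out of the analysis. Under 7.B.3.1, a patient withdrawn after entering follow-up stays in the ITT set, and the hospital days after the exit are what is lost. For exits before Visit 2 the protocol's own sample-size reasoning assumes no usable primary data.

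No size can be derived from the documents. They give neither the frequency of discretionary exits, nor their split by arm, nor the later hospital use of those who leave. A figure in days obtained by assuming a rise in hospital use after withdrawal would rest on invented rates. It would also be a shift in means, which does not translate directly into the rank-based primary test. The illustration marks the range under its stated assumptions: a two-sided error of about 5.6% to 6.3% if exits are unrelated to risk, and about 9% to 20.5% in the adverse case.

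**What to change.** Reconcile 4.B.5 with 3.D, and align the wording of 4.B.4, so that an investigator's judgement that procedures are compromised does not by itself end data collection. State that, after any such decision, hospital admission and discharge dates are collected to Month 12 by visit, telephone or medical record unless the patient withdraws consent. Survival to Month 12 is already covered in 3.D. Whether the allocated strategy continues is a separate decision, and this change need not touch it.

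Cost: a sentence or two in an amendment and a little extra follow-up. Most of that is already foreseen in 3.D, and the quarterly visits and the telephone interviews between them (4.B.3.2) provide the means.
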